---

## ◆ Summary of Protocol

Title	An Open Label, Multicenter, Retrospective, Pivotal Trial to Evaluate the Efficacy of Clinical Decision Support System-mPDia for Neurodegenerative Parkinsonism using MRI images					
Institution	10 hospitals consisting of Gachon University Gil hospital et. al (Gangnam Severance Hospital, Kyung Hee University Hospital, Korea University Guro Hospital, Korea University Ansan Hospital, Seoul St. Mary's Hospital, Seoul Asan Hospital, Hallym University Dongtan Sacred Heart Hospital, Hallym University Pyeongchon Sacred Heart Hospital, CHA Bundang Medical center)					
Investigational Device	Product name: mPDia Item Name: Clinical Decision Support System Manufacturer: Heuron Co.,Ltd					
Purpose	This trial is to check if the diagnosis results of mPDia would meet the success criteria, which is the lower limit of the 95% confidence interval satisfying 88.2% sensitivity and 70% specificity, while using final clinical diagnosis results of medical specialist groups as a golden standard. When the success criteria of mPDia, which is established based on prior reported sensitivity and specificity of neurodegenerative Parkinsonism diagnosis research, is satisfied, it is determined to have efficacy in assisting diagnosis of Parkinsonism.					
Design	Open label, Multicenter, Retrospective, Pivotal clinical trial					
Target case amount	
Total of 221 cases
 
The sensitivity and specificity goal were set as 95% and 86%, respectively, and the lower limit of the 95% confidence interval, which is the success criteria of this study, was calculated as 88.2% and 70%, respectively. The necessary case (image) amount for calculation was 144 people and 56 people. Considering the 10% dropout rate, 159 people for the patient group and 62 people for the normal group, which is 221 people in total, was calculated.
 
  
 Clinical performance target (<math>P_1</math>)	Least clinical performance (= lower limit of 95% confidence interval) (<math>P_0</math>)	N	+10% dropout rate	Total	
  
	Clinical performance target ( $P_1$ )	Least clinical performance (= lower limit of 95% confidence interval) ( $P_0$ )	N	+10% dropout rate	Total
Clinical performance target ( $P_1$ )	Least clinical performance (= lower limit of 95% confidence interval) ( $P_0$ )	N	+10% dropout rate	Total		

	
 
 Sensitivity: 0.950	Sensitivity: 0.882	144	159		
 
 Specificity: 0.860	Specificity: 0.700	56	62	221	
 
	Sensitivity: 0.950	Sensitivity: 0.882	144	159		Specificity: 0.860	Specificity: 0.700	56	62	221
Sensitivity: 0.950	Sensitivity: 0.882	144	159								
Specificity: 0.860	Specificity: 0.700	56	62	221							
Inclusion Criteria and Exclusion Criteria	
1. Inclusion Criteria
 
Normal group
 
 
1) Adult more than 19 years old
 
2) Person with confirmed 3T nigrosome 1 MRI image
 
3) Person with confirmed normal <math>^{18}\text{F}</math> FP-CIT PET/CT image
 
4) Research participant who visited clinic with parkinsonian symptom as chief complaint that did not correspond to neurodegenerative parkinsonism or healthy participant.
 
 
Patient group
 
 
1) Adult more than 19 years old
 
2) Person with confirmed 3T nigrosome 1 MRI image
 
3) Person with confirmed abnormal <math>^{18}\text{F}</math> FP-CIT PET/CT image
 
4) Person who visited clinic with parkinsonian symptom as chief complaint and was diagnosed as neurodegenerative parkinsonism (multiple system atrophy parkinsonian type, progressive supranuclear palsy).
 
 
2. Exclusion Criteria
 
 
1) Patient with encephalopathy besides parkinsonism.
 
2) Person with anatomic abnormality confirmed by MRI etc.
 
3) Person with other causative disease in advance. (ex: thyroid disease)
 
4) Patient with lesion in basal ganglia such as in Vascular Parkinsonism, Hydrocephalus, Wilson's disease.
 
5) Other cases that the researcher determines to be unsuitable for this clinical trial.
 
 
* Specific reason will be documented in the case report form
										

Data collecting method	
The following data will be collected retrospectively from person whose past 3T nigrosome 1 MRI image, F FP-CIT PET/CT image, image interpretation, and neurologic exam results are confirmed by medical records, and those whose diagnosis as neurodegenerative parkinsonism is confirmed.
 
Data collecting must be executed following the protocol 10.2 random collection. Only the verified researcher who is registered in this study will have access to medical records. Data collected for this study will be as follows:
 
 
- Demographic information
 
- Environmental factor and medical history/past history
 
- Family history
 
- MDS-UPDRS assessment results
 
- Check Red Flag signs suggestive of PD plus syndrome
 
- Non-motor symptom assessment scale results of Parkinson's disease
 
- REM sleep behavior disorder screening results
 
- Check of any pain
 
- Cognitive function test (K-MMSE, K-MoCA) results
 
- S&E ADL test results
 
- Hoehn & Yahr stage test results
 
- F FP-CIT PET/CT image and interpretation results
 
- Results of neurologic exam and decision of neurodegenerative parkinsonism
 
- Confirmed 3T nigrosome 1 MRI image
 
 
Data used in this study have been collected by the 10 participating institutions from May 1st, 2018 to the starting period of the clinical trial. Data used for the education of the investigational device were collected from November 1st, 2014 to April 30th, 2018 by one institution (Gachon University Gil Hospital), making it mutually independent.

------------------------	--


Study Method
	<pre> graph LR     A[Retrospective random data collection] --> B[Exclusion Criteria]     B --> C[Suitable]     B --> D[Unsuitable]     C --> E[Blinding (Blinding coordinator of each institution)]     D --> F[Preparation of Golden Standard]     E --> G[Independent execution]     E --> H[Interpretation of neurodegenerative parkinsonism by software (normal/abnormal)]     G --> I[Independent interpreter of each institution]     H --> I     I --> J["(Independent statistician)"]     J --> K[Calculation of sensitivity/specificity of investigational device]   </pre> 
1. Image blinding
 
The blinding coordinator will select 3T nigrosome 1 MRI image from data collected by the 10.1 data collection method and blind all non-image information such as the belonging group or demographic information.
 
2. Interpretation using mPDia
 
The blinded image will be delivered to an independent interpreter and the interpreter will sequentially upload the image on mPDia according to the image number, check the result, and save it. The saved results will be printed to be used as source document. The results should be blinded, so the saved and printed results should have separate passwords or be in a locked space so that researchers other than the independent interpreter have no access. The independent interpreter should be a neurologist or radiologist of each site who is not participating in this study and should be educated of mPDia usage for this study. Interpretation using mPDia should be performed independently from golden standard creation, and an independent statistician of the sponsor collects the mPDia interpretation data.
 
3. Golden Standard
 
[name], a neurologist of Gachon University Gil Hospital, [name], a radiologist of Gachon University Gil Hospital, will check the collected medical records, provide final diagnosis to the registered candidate based on protocol 10.5.1 neurodegenerative parkinsonism diagnosis checklist and check on the following

---------------------	--

	
neurodegenerative parkinsonism classification chart. Cases corresponding to Parkinson's disease or atypical Parkinsonian syndromes are defined as neurodegenerative parkinsonism diagnosis. Besides such cases, it is defined not to be neurodegenerative parkinsonism. Only when corresponding to neurodegenerative parkinsonism can the positive response of mPDia regarding neurodegenerative parkinsonism be confirmed. The following diagnosis results will be used as a golden standard in this study.
 
1) Positive in neurodegenerative parkinsonism 2) Negative in neurodegenerative parkinsonism
 
When opinions of two specialists are different, the two will discuss to reach a consensus and record it on the final diagnosis result. All discussed contents will be documented on the Note to file. Golden standard creation must be performed independently from mPDia interpretation, and the golden standard data will be collected by an independent statistician of the sponsor.
 
4. Independent statistician
 
The independent statistician of this study will be Doctor [name] of Heuron Co.,Inc. Without participating in this study, the independent statistician will collect mPDia interpretation results and golden standard and save them in a separate hardware which only the independent statistician can have access to. The independent statistician cannot open the interpretation results or golden standard before statistical analysis is finished.

Study Period	12 months from IRB approval date
Endpoint	
1. Efficacy endpoint Sensitivity and specificity of mPDia for diagnosis of neurodegenerative parkinsonism using final diagnosis results of the specialist group as a golden standard
 
2. Efficacy endpoint assessment method

With the following calculation methods, sensitivity and specificity are calculated, and the 95% confidence interval is provided and evaluated to assess whether the lower limit of the 95% confidence interval reaches 88.2% sensitivity and 70% specificity, which is the success criteria of mPDia, in comparison to the golden standard, which is the final clinical diagnosis result of the specialist group for diagnosis of neurodegenerative parkinsonism.

< Sensitivity and specificity calculation method >

Results	Golden standard			True positive + False positive
	Positive	Negative	Total	
Investigational Device (mPDia)	Positive	True positive (TP)	False positive (FP)	True positive + False positive
	Negative	False negative (FN)	True negative (TN)	False negative + True negative
	Total	True positive + False negative	False positive + True negative	N

- Sensitivity:  $100 \times \text{True positive (TP)} / [\text{True positive (TP)} + \text{False negative (FN)}] (\%)$
- Specificity:  $100 \times \text{True negative (TN)} / [\text{False positive (FP)} + \text{True negative (TN)}] (\%)$

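### Minor: the 10% dropout allowance was added to the required numbers (N × 1.1) instead of dividing by 0.9, so 159 + 62 = 221 falls just short of covering a 10% loss

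*Combined protocol and SAP*

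**What the plan says.** The sample size appears in the Combined protocol and SAP, Summary of Protocol, row Target case amount, as a short text followed by a table.

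- **Numbers needed for analysis:** "The necessary case (image) amount for calculation was 144 people and 56 people", for the patient group (sensitivity) and the normal group (specificity) respectively.
- **Numbers to collect:** "Considering the 10% dropout rate, 159 people for the patient group and 62 people for the normal group, which is 221 people in total".
- **Table:** the rows read "Sensitivity: 0.882 144 159" and "Specificity: 0.700 56 62 221". The column holding 159 and 62 is headed with a plus sign in front of "10% dropout rate".
- **Performance assumptions:** "The sensitivity and specificity goal were set as 95% and 86%, respectively". The success criterion is "the lower limit of the 95% confidence interval satisfying 88.2% sensitivity and 70% specificity".

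The Summary shows no formula for the dropout step. It also states no power.

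**The concern.** A dropout rate is normally a proportion of the cases collected. To keep N evaluable cases after losing a fraction d, one collects N/(1 − d). Adding 10% to N instead gives 1.1 × N, and losing 10% of that leaves 1.1 × 0.9 × N = 0.99 × N, which is 1% short. Rounding up can hide such a gap; here it does not in either group.

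What is at stake is the consistency of a pivotal trial's stated target. The plan gives the numbers it needs, the loss it expects and the number it will collect, and the three do not agree. The effect on the trial's result is very small, as the power figures below show.

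**Working it through.** **Inputs** (all from Summary of Protocol, Target case amount): required N = 144 and 56; dropout rate 10%; printed targets 159, 62 and 221; expected sensitivity 0.95 and specificity 0.86; minimum values 0.882 and 0.70.

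**1. Reproducing the printed targets, N × 1.1**
- Patients: 144 × 1.1 = 158.4 → 159
- Normals: 56 × 1.1 = 61.6 → 62
- Total: 159 + 62 = 221

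All three match.

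**2. What a 10% loss leaves**
- 159 × 0.9 = 143.1, which is 0.9 below 144
- 62 × 0.9 = 55.8, which is 0.2 below 56

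In whole cases, the largest losses that still leave 144 and 56 are 15 of 159 (9.4%) and 6 of 62 (9.7%). Both are under 10%.

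**3. Targets that cover 10%, N/(1 − 0.10)**
- 144/0.9 = 160, and 160 × 0.9 = 144.0
- 56/0.9 = 62.2 → 63, and 63 × 0.9 = 56.7
- Total: 160 + 63 = 223, two more than printed

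**4. The rate that the printed targets do cover**
- 1 − 1/1.1 = 0.0909
- 144/0.91 = 158.24 → 159 and 56/0.91 = 61.54 → 62, total 221

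In steps of 0.1 percentage point, every rate from 8.9% to 9.4% gives this same pair, and 10% does not.

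**5. Chance of keeping the required numbers**, assuming each case is lost independently with probability 10% (an assumption; the plan gives no loss model):

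| Group | Required | Collected as printed | Collected at N/0.9 |
|---|---|---|---|
| Patients | 144 | 159: 0.47 | 160: 0.57 |
| Normals | 56 | 62: 0.57 | 63: 0.71 |

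**6. Effect on power.** The Summary states no power, so the setting has to be inferred. The one-sample normal-approximation formula is

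N = [z(α) √(P0(1 − P0)) + z(power) √(P1(1 − P1))]² / (P1 − P0)².

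At two-sided 5% and 80% power it gives 143.9 → 144 and 55.3 → 56, which are the plan's own numbers. In that setting, losing one case changes power as follows:
- Sensitivity: 0.800 at 144, 0.797 at 143
- Specificity: 0.806 at 56, 0.797 at 55

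Exact binomial power moves in steps as N changes, and the Summary does not name the interval method:

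| Endpoint | N | Clopper-Pearson limit | Wilson limit |
|---|---|---|---|
| Sensitivity | 143 | 0.820 | 0.820 |
| Sensitivity | 144 | 0.815 | 0.815 |
| Specificity | 55 | 0.765 | 0.765 |
| Specificity | 56 | 0.748 | 0.847 |

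One more case slightly lowers exact power for sensitivity. For specificity it lowers power under one method and raises it under the other.

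**The case against.** The strongest reply is that the table does what its label says. A column headed with a plus sign and 10% contains N plus 10%, rounded up, and every printed number follows. The text does not say what the 10% is a percentage of, so N × 1.1 could be called a convention. This explains how the figures arose, and that part stands. It does not settle the matter, because the sentence above the table speaks of a dropout rate, and adding 10% to N does not cover a 10% dropout.

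Several further points carry some weight:

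- **The shortfall is a fraction of a case.** Correct: 0.9 and 0.2 of a case on expectation. Moreover, 160 and 63 do not guarantee the required numbers either; under the independent-loss assumption they miss them with probability 1 − 0.57 = 0.43 and 1 − 0.71 = 0.29. But N/0.9 does meet them on expectation, which is what the allowance is for.
- **The small power loss is shown only by the approximate formula.** Also correct. For specificity, exact power at 56 compared with 55 is 1.8 points lower (Clopper-Pearson) or 8.2 points higher (Wilson). The direction depends on the method, so the extra cases cannot be said to give a dependable gain.
- **The 9% is fitted backwards.** It is: the plan never mentions 9%. It is offered only as the rate that the printed sizes support.
- **Collection is retrospective, and the Summary does not say whether excluded cases are replaced.** True, and replacement might make the allowance moot in practice. It would not make the stated rate and the stated target agree.

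**Conclusion.** The point holds, as a minor arithmetic correction. With the dropout rate read as a share of the cases collected, 159 and 62 leave an expected 143.1 and 55.8 after a 10% loss, below the 144 and 56 that the plan calls necessary. The correct target at 10% is 223, not 221: one more case in each group.

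This conclusion rests only on printed figures and simple arithmetic. The retention probabilities also need the independent-loss assumption. The power figures also need the inferred setting of a two-sided 5% level, which reproduces the plan's N at 80% power. On that basis the cost is under 1 percentage point of formula power per endpoint, with no consistent direction in exact power. The design is not in question.

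**What to change.** Choose one of two corrections and make it in both the text and the table under Target case amount:

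1. Keep the 10% rate and restate the target as 160 patients + 63 normals = 223, calculated as N/0.9.
2. Keep 159 + 62 = 221 and restate the allowance as 9%, calculated as N/0.91.

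If 10% is the sponsor's real expectation of loss, the first is the consistent choice; the second fits only if the sponsor is content to plan for 9%. Either way, state the formula and reword the column heading so that it is clear the percentage applies to the cases collected.

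The first option costs two more archived cases and the second none. Endpoints, success criteria and analysis stay as they are.

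### Patient-group inclusion item 4 names only MSA-P and PSP, while the golden standard defines the same term as Parkinson's disease or atypical Parkinsonian syndromes

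*Combined protocol and SAP*

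**What the plan says.** All references are to the Summary of Protocol.

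- **Inclusion Criteria, Patient group, item 4:** the person presented with parkinsonian symptoms and was "diagnosed as neurodegenerative parkinsonism (multiple system atrophy parkinsonian type, progressive supranuclear palsy". Item 3 also requires an abnormal FP-CIT PET/CT.
- **Inclusion Criteria, Normal group, items 3 and 4:** a normal FP-CIT PET/CT, and either "parkinsonian symptom as chief complaint that did not correspond to neurodegenerative parkinsonism or healthy participant".
- **Study Method, 3. Golden Standard:** "Cases corresponding to Parkinson's disease or atypical Parkinsonian syndromes are defined as neurodegenerative parkinsonism diagnosis". The next sentence closes the definition: "Besides such cases, it is defined not to be neurodegenerative parkinsonism".
- **Data collecting method:** the source records include "those whose diagnosis as neurodegenerative parkinsonism is confirmed", with no subtype named. The items collected include a non-motor symptom scale for Parkinson's disease and a check of red flags for PD plus syndrome.
- **Endpoint, 1. Efficacy endpoint:** "Sensitivity and specificity of mPDia for diagnosis of neurodegenerative parkinsonism", judged against the golden standard.
- **Purpose:** meeting the success criteria is taken as efficacy in assisting diagnosis of Parkinsonism. The criteria are said to come from earlier research on diagnosing neurodegenerative Parkinsonism.

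**The concern.** Item 4 decides which records enter the sensitivity denominator, and the golden standard decides what a positive case is. If entry is narrower than the reference standard, the trial can meet its sensitivity criterion and support a claim about neurodegenerative parkinsonism as a whole without testing the device in Parkinson's disease, the first diagnosis that the reference standard names. The two specialists who set the golden standard classify registered candidates only, so they cannot restore cases that were never selected, and no later analysis can either.

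The ambiguity also matters if the parenthesis was meant as examples. Ten hospitals select from existing records. Some could read item 4 as a limit and others as an illustration, and the case mix would then differ between sites for a reason unrelated to the device.

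**Working it through.** **The plan's own figure.** The available text gives P0 and P1 but neither the power nor the formula. The standard one-sample formula, with two-sided 5% and 80% power assumed, is

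N = [1.960·√(P0(1−P0)) + 0.842·√(P1(1−P1))]² / (P1−P0)²

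- Sensitivity, P0 = 0.882 and P1 = 0.950: N = 143.90, rounded up to 144. Then 144 × 1.1 = 158.4, rounded up to 159.
- Specificity, P0 = 0.700 and P1 = 0.860: N = 55.34, rounded up to 56. Then 56 × 1.1 = 61.6, rounded up to 62.
- Total: 159 + 62 = 221.

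These match the plan. The formula uses one sensitivity for the whole patient group and no subtype mix. The choice of definition therefore does not alter 144 or 159; it alters which population the estimate describes.

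**The definitions side by side.** The rest is a comparison of text. MSA-P and PSP are taken to be atypical Parkinsonian syndromes.

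| Case | Patient group (item 4 read literally) | Normal group | Golden standard |
|---|---|---|---|
| MSA-P or PSP, abnormal PET | Eligible | No | Positive |
| Parkinson's disease, abnormal PET | Not eligible: not listed | No: needs a normal PET and no neurodegenerative parkinsonism | Positive |
| Other atypical syndrome, abnormal PET | Not eligible: not listed | No, for the same reasons | Positive |
| Parkinsonian symptoms, not neurodegenerative, normal PET | No | Eligible | Negative |

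1. The second and third rows show the gap: cases that the reference standard calls positive have no route into the trial. Read literally, 0 of the 144 required positives (0 of 159 with dropout) would have Parkinson's disease.
2. The first row shows the limit of the problem. The item 4 list lies inside the golden-standard definition, so an enrolled MSA-P or PSP case is not misclassified and sensitivity can be calculated.
3. Is the parenthesis a list or a set of examples? The exclusion criteria mark their examples: "Person with other causative disease in advance. (ex: thyroid disease" and "lesion in basal ganglia such as in Vascular Parkinsonism". Item 4 carries no such marker. That favours a list, but only weakly.
4. The data items point the other way. A Parkinson's disease non-motor scale, and red flags whose use is to raise suspicion of PD plus syndrome, suggest that Parkinson's disease cases were expected.
5. The available text gives no subtype sensitivities and no expected case mix, so no effect on sensitivity can be computed, in size or in direction.

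**The case against.** The strongest reply is that this is a drafting slip. The golden standard expressly includes Parkinson's disease, the data items suit a Parkinson's disease population, and the document is loosely worded elsewhere, so a missing marker for examples proves little. An omission in translation cannot be ruled out. The purpose, endpoint and source-population statements need not repeat entry limits, so their silence on subtypes is not a separate contradiction. Sections 10.2 and 10.5.1 and the classification chart are not in the available text and may settle the matter.

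Much of this stands. It lowers confidence in the consequence, but it does not remove the mismatch. If Parkinson's disease was intended, item 4 is incomplete as written, and the sites could apply it in different ways.

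Three stronger readings are tempting and not supported:

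- *The trial will contain no Parkinson's disease.* This requires the parenthesis to be exhaustive, and the data items suggest otherwise.
- *Sensitivity will be biased, or cases misclassified.* The definitions are nested, and nothing in the documents gives the sign or size of an effect.
- *The sample size is wrong.* It reproduces from P0 and P1 under the assumptions shown and does not depend on the subtype list.

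**Conclusion.** The point holds as an internal inconsistency in a definition that governs eligibility. Item 4 as written is narrower than the golden standard for the same term, and no available passage reconciles them. Confidence in that is high.

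The consequence depends on how item 4 is applied. Read literally, the primary sensitivity describes MSA-P and PSP only, while the endpoint and claim are broader. Read as examples, the risk is uneven selection across sites. Confidence in the consequence is moderate, because the data items suggest that Parkinson's disease was intended and because the sections that might clarify the list could not be checked.

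It should be corrected before cases are selected, since the case spectrum cannot be repaired at analysis.

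**What to change.** Before selection from the records begins, make one definition govern entry, golden standard, endpoint and claim. The intended scope is the sponsor's to state.

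- **If the whole of neurodegenerative parkinsonism is intended,** replace the two diagnoses in the item 4 parenthesis with the golden-standard definition (Parkinson's disease or atypical Parkinsonian syndromes). This is one line.
- **If only MSA-P and PSP are intended,** leave the golden-standard definition as it is. Narrowing its positive class while keeping the sentence that makes all else negative would turn Parkinson's disease into a golden-standard negative, and would change the meaning of normal-group item 4, which uses the same term. Instead, limit the purpose, endpoint and conclusion to MSA-P and PSP. Confirm that the 88.2% bar, drawn from research on neurodegenerative Parkinsonism, applies to those two diagnoses, and that the ten sites hold 159 such records. This costs more than a line of text.

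In either case, check the wording against sections 10.2 and 10.5.1 and the classification chart. If one of them already settles the scope, carry that definition into item 4. The sample size stays at 144 (159 with dropout) for the patient group as long as P0 and P1 are unchanged.

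### Exclusion item 5 allows open-ended removal of cases before blinding, so difficult images could leave the test set by judgement

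*Combined protocol and SAP*

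**What the plan says.** All references are to the Summary of Protocol.

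- **Exclusion Criteria.** Items 1 to 4 name clinical or anatomical reasons. Item 5 is open: "Other cases that the researcher determines to be unsuitable for this clinical trial". A note below the list adds "Specific reason will be documented in the case report form".
- **Data collecting method.** Collection is to be random: "Data collecting must be executed following the protocol 10.2 random collection". The collected record includes the neurologic exam with the parkinsonism decision, the PET/CT image with its interpretation, and the 3T nigrosome 1 MRI. On access: "Only the verified researcher who is registered in this study will have access to medical records".
- **Study Method, flow chart.** The first box is "Retrospective random data collection". It leads to the exclusion criteria, and cases found suitable go on to "Blinding (Blinding coordinator of each institution").
- **Study Method, image blinding.** The blinding coordinator works on data already collected, and is to "blind all non-image information such as the belonging group or demographic information". mPDia is run on the blinded images afterwards by an independent interpreter, and the results are kept from the other researchers.
- **Success rule.** The lower 95% confidence limit must reach 88.2% for sensitivity and 70% for specificity. Planned evaluable numbers are 144 patients and 56 normals.

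**The concern.** In a prospective trial a catch-all exclusion protects participants and is used before any outcome exists. Here the scans and diagnoses already exist and nobody is exposed to anything, so that purpose is absent. What remains is a discretionary filter, placed after the random draw and before the mask, used by someone who can know the correct answer and has access to the image that the device will read.

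No bad faith is needed. A researcher may sincerely find a patient with a preserved-looking nigrosome, or a normal subject with an apparent loss, unsuitable. If such cases are also those that mPDia tends to misread, removing them takes expected false negatives and false positives out of the two tables. Both endpoints then move towards success. A random draw that comes earlier cannot prevent this, and a recorded reason shows the removal without undoing it.

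**Working it through.** **1. The plan's own figures.** Inputs from the target case section: P0 = 0.882 and P1 = 0.95 for sensitivity; P0 = 0.70 and P1 = 0.86 for specificity. Two-sided 5% follows from the 95% interval. Power of 80% is assumed, because the text available gives none.

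n = [1.960·√(P0(1−P0)) + 0.842·√(P1(1−P1))]² / (P1−P0)²

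- Sensitivity: [1.960 × 0.3226 + 0.842 × 0.2179]² / 0.068² = 143.9, so 144.
- Specificity: [1.960 × 0.4583 + 0.842 × 0.3470]² / 0.16² = 55.3, so 56.

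Both match the plan. The sample size is not at issue.

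**2. Counts needed to pass.** The text available does not name the interval method, so Clopper-Pearson is assumed.

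- Sensitivity: 135/144 is needed (lower limit 88.5%; 134/144 gives 87.6%).
- Specificity: 47/56 is needed (lower limit 71.7%; 46/56 gives 69.6%).

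**3. Effect of selective removal.** Let f be the share of would-be misread cases that is removed before blinding. It is an assumption; the documents give no value. Assume also that no would-be correct case is removed, that removed cases are replaced so that 144 and 56 are kept, and that true performance p equals P0. Then:

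- apparent rate q = p / [p + (1−p)(1−f)]
- number screened = n / [1 − f(1−p)], so number removed = n·f(1−p) / [1 − f(1−p)]
- chance of a false pass = P(X ≥ required count), X binomial (n, q)

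| Endpoint | f | q | Cases removed | False pass |
|---|---|---|---|---|
| Sensitivity | 0 | 0.882 | 0 | 2.0% |
| Sensitivity | 0.2 | 0.903 | about 3.5 of 147.5 | 10% |
| Sensitivity | 0.4 | 0.926 | about 7.1 of 151.1 | 37% |
| Specificity | 0 | 0.700 | 0 | 1.3% |
| Specificity | 0.2 | 0.745 | about 3.6 of 59.6 | 6.6% |
| Specificity | 0.4 | 0.795 | about 7.6 of 63.6 | 27% |

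With the Wilson interval the sensitivity rows are unchanged (135/144 is still needed). Specificity needs 46/56, and its false-pass chances become 2.9%, 12% and 39%. Each figure is for one endpoint taken alone.

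**The case against.** The strongest reply is that the excluding researcher does not know which cases mPDia will misread. The device is run after blinding, by an interpreter outside the study, with results locked away. This stands, and it rules out a stronger reading that a reader might infer: that a handful of removals decides the trial. The arithmetic for that reading is correct. By Clopper-Pearson, 132/144 has a lower limit of 85.9% and 132/141 one of 88.2% (0.8823 against 0.882); 45/56 gives 67.6% and 45/54 gives 70.7%. But it removes exactly three false negatives and two false positives, which nobody can identify at that step. It starts from counts chosen just below the line, and it assumes that removed cases are not replaced.

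Three further points stand in part.

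- The documents give researchers access to the MRI, but do not say that its appearance is used when item 5 is applied. Use of the image is possible, not stated. Nothing shows that selection took place or was intended.
- Sections 10.1 and 10.2 are cited but were not available for review. They could regulate replacement, logging or who decides.
- The required reason makes each removal auditable. However, the text available describes no masked review, no reporting of exclusions by group, and no analysis that restores them.

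The extracted flow chart also has a doubtful arrow, from unsuitable cases to preparation of the reference standard. The order relied on here does not depend on it, since the path from exclusion through suitable cases to blinding is clear.

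**Conclusion.** The concern holds as a design risk. A written rule lets a person with access to the diagnosis, PET reading and test image remove cases by judgement before blinding, and both endpoints depend on the cases that remain. The direction of any bias is towards success, provided that visible image or diagnostic difficulty predicts mPDia errors. Its size cannot be fixed from the documents. Over an assumed f of 0 to 0.4, with performance exactly at the failing bound, the chance of a false pass runs from 2.0% to 37% for sensitivity and from 1.3% to 27% for specificity (Clopper-Pearson). If difficulty as the researcher sees it is unrelated to device error, there is no such bias. The clause serves no protective purpose in an archive study and is cheap to tighten, so it should be changed, subject to what sections 10.1 and 10.2 already provide.

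**What to change.** Replace item 5 with a closed list, fixed before case selection, containing two kinds of reason:

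- **Record-based reasons**, for example a duplicate record.
- **Objective technical reasons**, for example an incomplete acquisition or a file that mPDia cannot process. These are judged by someone masked to group, such as the blinding coordinator after blinding.

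Add a rule for any randomly drawn case that meets the inclusion criteria, triggers none of exclusion items 1 to 4, and is removed all the same. Such a case is logged by group and site with its reason, given a reference-standard diagnosis where the records allow, run through mPDia, and added back in a sensitivity analysis of both sensitivity and specificity. If sections 10.1 or 10.2 already contain part of this, the Summary should point to it.

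The cost is protocol wording, a little extra reading for the two specialists and the independent interpreters, and one further analysis. Stated accuracy may be slightly lower because some awkward cases stay in.
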